Intention: 6 items are used to assess intention for physical activity. We used the 3 items that have been used in the PESS study and added 3 items that [name] commonly uses in his research. Questions pertain to women’s intentions, motivation, and plans to be physically active each day in the next week. Responses range from 1 (strongly disagree/definitely not/not at all) to 7 (strongly agree/definitely/very much).

K. Weight Beliefs Measures

i. Pregnancy Weight Gain Attitude Scale: The PWGAS is an 18-item questionnaire developed by Palmer, Jennings, & Massey (1985), to evaluate and assess plausible attitudes of pregnant women towards their weight gain during pregnancy. A Likert scale is used ranging from 1 (strongly agree) to 5 (strongly disagree). The scores on individual statements are summed to yield a composite score. Higher total scores indicate a more positive attitude towards gaining weight in pregnancy while lower scores indicate a more negative attitudes towards pregnancy weight gain.

L. **Bloodwork**: Blood work will be obtained according to standard CRC procedures and our established assays once at baseline and once in the third trimester of pregnancy. Less than 25 cc’s of blood will be drawn by trained nursing staff. Participants do not need to be fasting. We will ask participants two questions at the time of each blood draw: 1) what time did you eat last? And 2) what did you eat? These biomarkers are linked to metabolic syndrome (and may be exacerbated in pregnancy due to high GWG) and thus, they will be important outcomes of the future RCT. The biomarkers selected for

analysis (listed below) have been linked to fetal growth, metabolic syndrome and cardiovascular disease, which may be exacerbated in pregnancy due to high GWG or postpartum weight retention. The blood biomarker measurements that we will be assessing are as follows: Iron, CRP, Vitamin A, Vitamin D, Folate, Zinc, Selenium and Copper. Blood will be centrifuged and aliquotted by a trained research technician using standard biohazard safety procedures. Samples will then be frozen at -80° C. Once all samples have been collected, they will be transported on dry ice to selected laboratories for analyses.

M. Urine: Urine samples will be collected weekly during the prenatal period to assess basal cortisol level as it relates to stress. Participants will be asked to collect voided urine overnight, starting from the time participant falls asleep and ending with the last collection being first morning void after waking for the day. We will provide 1 collection container for whole the whole study for storage of all urine. We will also provide a urine collection hat for easy collection. Participants will track time they went to bed, time of any/all collections overnight and time of first morning void. Participants may keep the urine collection container beside the toilet/in the bathroom overnight, and will be asked to refrigerate after first morning void until time of study visit, when they will bring urine collection container with them. We will provide a zip-top plastic bag for transportation. Study staff will process the urine samples in the CRC, following biohazard safety protocols. Urine samples for analysis will be transferred to cryovials by pipette and frozen in a -20 degree freezer located in the CRC. Cryovials will be labeled with participant ID # and date only (i.e. no personally identifying information). Once all samples have been collected, a research study staff member will transport samples to the Biobehavioral Core Lab for processing. Urinary free cortisol (UFC) and creatinine levels will be measured and UFC/creatinine ratio (Cort/Cr) calculated.

N. Adiposity (Body Composition)

Standard CRC procedures will be used to assess:

- i. Maternal waist circumference using an inelastic tape in area between ribs and iliac crest and recorded to nearest 0.1 cm
- ii. Skin fold Thickness measured at five sites per the Anthropometric Standardization Reference Manual⁷⁵
- iii. Air-displacement Plesmography [BOD POD; Life Measurement, Inc, Concord, CA) measuring weight (mass) and volume to calculate body density (mass/volume) and percent body fat. (PeaPod for infants)]

O. Dietary Intake

- i. Remote Food Photography Method: The Remote Food Photography Method[®] (RFPM) and the SmartIntake[™] smartphone app were developed by [name]., H. [name]. and colleagues at the Pennington Biomedical Research Center as a way to accurately measure the energy intake of adults in free-living conditions. RFPM has been validated and is currently used in multiple studies across the country. Using a smartphone, participants capture images (photos) of all food and beverages consumed both prior to consuming the meal or snack and of the leftover food or beverage that was not consumed. These images and accompanying food identifier data (e.g., barcodes, PLU numbers, food descriptions) are emailed to Pennington Biomedical Research Center (PBRC) and are stored in the Automated Data Management Utility (ADMU). These images are used to estimate energy intake by trained PBRC staff.
- ii. MyFitness Pal: Web-based and smartphone app dietary intake tracker. Participants will have accounts created for them and will record their diets 3days/week.

P. Metabolism

- i. The Breezing Device: An indirect calorimetry analyzer that measures the rate of oxygen consumption and carbon dioxide production and determines how much energy the body is burning

due to the metabolism of nutrients (named Resting Energy Expenditure, REE), and the type of nutrients the body uses to produce energy (Energy source = respiratory quotient, RQ). Developed at Arizona State University. The Breezing is a cellphone-size, battery operated, portable technology that syncs with smartphones. This tracker takes a traditional laboratory-based measurement and makes it faster, more affordable and mobile. Breezing has a 99.8% correlation with the gold standard method, Douglas Bag (Forzani, Tao, et.al., Clinical Nutrition, 2013).

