Although this scan is non-diagnostic in nature, following each, indicators of fetal growth collected by fetal ultrasound will be sent by [name] (Co-I, OBGYN) at Hershey Medical Center within 24-72 hours to ensure safety of mother-infant dyads. [name] will complete a Review Form for each scan to verify that the scan was reviewed and will highlight any potential medical issues that may be impacting gestational weight gain or infant weight. [name] will send the review forms to study research staff, who will then hand deliver to participant's physician. Review forms with potential abnormalities noted will be delivered right away, while review forms with normal growth will be delivered to the practice on a weekly basis.

Visits B: Intervention Sessions and Weekly Assessments. During the intervention, all participants will start out at the Baseline level. The baseline level will last 2 weeks and there will be an assessment to determine weight gain over those 2 weeks (See Appendix C for description of adaptive steps). If weight gain has succeeded the recommended amount, participants will be adapted up to a new level of intervention. After every 4 weeks, an assessment will be performed and adaptations up will be made if necessary. The adaptations are as follows:

1. Baseline: one 30-min face to face session with intervention leader for education and guidance (self-monitoring, goal-setting) on GWG, HE, and PA and daily HE/PA self-monitoring (i.e., keeping track daily of their activity and eating patterns in a diary and completing the MyFitness Pal program either online or via a mobile phone app on 3 days per week (Please see Appendix D for outline of education content). The face-to-face session will take place in 128/208/223 Noll Laboratory. The written scripts for these intervention sessions and handouts are attached in the document section of CATS and labeled by week. The forms used to assess fidelity monitoring of these sessions are also attached in the

documents section. Participants are encouraged to get 150 min of moderate to vigorous intensity physical activity.

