10.1 Periodic evaluation of data

Daily weight data will be collected for intervention monitoring. Weekly HE and PA behaviors, self-regulation, psychological well-being, motivational determinants of HE and PA, and weight behaviors will also be collected and used to inform the intervention counseling in the following week. Also, as described above, will also collect PA session data on symptoms monitoring at pre-exercise, 5-min, 15-min, 25-min, and post-exercise.

See attached protocol for unexpected or adverse events monitoring.

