Overweight	25–29.9	15–25	0.6 (0.5–0.7)
Obese (includes all classes)	30 and greater	11–20	0.5 (0.4–0.6)

*Body mass index is calculated as weight in kilograms divided by height in meters squared or as weight in pounds multiplied by 703 divided by height in inches.

†Calculations assume a 1.1–4.4 lb weight gain in the first trimester.

Modified from Institute of Medicine (US). Weight gain during pregnancy: reexamining the guidelines. Washington, DC. National Academies Press; 2009. ©2009 National Academy of Sciences.

It is theoretically possible that behavioral interventions designed to manage GWG in OW/OBPW could result in energy imbalance and insufficient weight gain. The pilot studies that serve as the foundation for the current study **did not** find an association between study interventions and these adverse events. However, we will be monitoring weight on a daily basis and examining GWG on a weekly basis and will consult with co-investigator, [name], OBGYN to identify

if a woman has insufficient weight gain for gestational week. Indicators of insufficient weight gain are, for example, weight loss of >3% in a week, or 0% weight gain in a 4-week cycle. OW/OPBW should gain, on average, .5 lb per week, so we will use this as a threshold to understand the context of the weekly GWG relative to her overall GWG and clinical insight. We will consult with the participants OBGYN provider and [name] to determine if the participant should be removed from the study for insufficient GWG.

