The study's informed consent document will include information indicating that the study team will communicate with the participant's OBGYN or Primary Care Provider. The study team will ensure that open lines of communication exist with the healthcare provider in addition to the weight monitoring and review. To establish the lines of communication between the study team and the PCPs, upon participant randomization, the participant is required to have a physician consent form completed to "clear her" for study participation. Healthcare providers will also be directly notified about their patient's participation in the study. A brief description of the study will be shared with them as well as a contact number to call the study team should the provider become concerned about insufficient GWG by their patient. Recognizing that weight monitoring is typically performed at all regularly scheduled primary care appointments, we will ask providers for their collaboration in monitoring prenatal weight gain in that we would like to be alerted to any concerns that their patient is demonstrating insufficient weight gain.

During each face to face visit, staff will calculate weight, BMI, and weight change. If the adverse risk for inadequate weight is identified, we will modify treatment (i.e., recommending increased energy intake). The PIs will review weight and applet data at least twice monthly and then contact the healthcare providers and co-investigator, [name] when appropriate after each individual is closely evaluated as described below. For any individual who meets initial screening criteria for weight gain concerns, numerous factors will be considered in determining whether the women's weight gain is problematic and/or related to study interventions. Examples of such factors include nausea, vomiting, and interval illness. If either the healthcare provider or the study investigators believe that it is possible that these growth patterns are a negative result from study participation, the women will be withdrawn from the study.

Co-Investigator, [name], our biostatistician, will include protocol compliance with inclusion and exclusion criteria, participant compliance with the interventions, and adverse events in consultation with the PI [name], Co-I, [name], and study staff ([name], [name]).

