24.0 Appendix

Appendix A. List of Measures and Descriptions

A. Weight, GWG, and Height

- i. Weight and GWG will be assessed: (1) pre- and post-intervention at the CRC using standard procedures (measured in duplicate to nearest kg using a high precision stand-on adult scale) and (2) daily at home using the FitBit Aria Wi-Fi Smart Scale (www.fitbit.com); weights will be wirelessly uploaded to online program). GWG will be standardized: target weight gain will be determined for each woman based on BMI status (OW = 15-25 lb, OB = 11-20 lb).¹ For the criterion measure to determine when to adapt the intervention, weight gain will be calculated to determine if a woman is gaining < her goal (-), at the exact amount of her goal (0), or > her goal (+). Pre-pregnancy weight and GWG from the first prenatal visit to the last pre-delivery weight will also be obtained from clinical records.⁷²
- ii. Height will be assessed at pre-and post-intervention with a stadiometer using standard CRC procedures.

B. Healthy Eating Behavior Measures

- i. Three Factor Eating Questionnaire: The Three Factor Eating Questionnaire is a 51-item questionnaire developed by Stunkard and Messick (1985) to measure three dimensions of human eating behavior: 1) dietary restraint, or cognitive control of eating behavior, 2) dietary disinhibition, or disinhibition of cognitive control of eating, and 3) susceptibility to hunger. We are only using 18 items of the revised TFEQ from Cappelleri (2009). These items are known as TFEQ-R18 as reported in (de Lauzon et al., 2004).

C. Physical Activity Behavior Measures

- i. Leisure Time Exercise Questionnaire: The Leisure-Time Exercise Questionnaire (LTEQ) is a 3 item questionnaire developed by Godin and Shephard (1985) to measure the amount and intensity of exercise a person engages in during a one week period. The LTEQ's original validated version is based on 15 minute bouts of leisure exercise. The LTEQ assesses the amount of strenuous (e.g., running, fast swimming), moderate (e.g., brisk walking, tennis), and mild exercise (e.g., easy walking, golf) that is done for at least 15-min during leisure-time in the past week. A total metabolic equivalent (MET) score is generated by multiplying the intensity level by the estimated rate of

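### Clinic weight is recorded only to the nearest kilogram before and after the intervention, which adds small avoidable error to measured weight gain; the precision of session weights and the source behind the weight flags are not stated

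*Combined protocol and SAP*

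**What the plan says.** GWG is the primary endpoint (section 1.2). Appendix A, item A, names two direct measurements of weight. The first is in the clinic: "Weight and GWG will be assessed: (1) pre- and post-intervention at the CRC using standard procedures", and these weights are "measured in duplicate to nearest kg using a high precision stand-on adult scale". The second is "daily at home using the FitBit Aria Wi-Fi Smart Scale", with no recording precision given. Weights from clinical records are a further source. The plan does not say how the duplicate clinic readings are combined.

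Appendix B, in the schedule of objective assessments, has a row for a standardized scale at the CRC or Noll Laboratory. It is marked at the onsite pre visit, weekly per session, and at the onsite post visit. The row gives no precision.

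Interval weight change is used in several places:
- Section 6.2, on stepping the intervention up: "After every 4 weeks, an assessment will be performed and adaptations up will be made if necessary".
- Section 10.2, on visits: "During each face to face visit, staff will calculate weight, BMI, and weight change".
- Section 10.2, on examples of insufficient gain: "weight loss of >3% in a week, or 0% weight gain in a 4-week cycle".

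On the weights used for monitoring, section 10.1 says "Daily weight data will be collected for intervention monitoring" and section 10.2 says "we will be monitoring weight on a daily basis and examining GWG on a weekly basis".

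**The concern.** A scale described as high precision is read to a whole kilogram, or 2.2 lb. Two readings minutes apart will nearly always round to the same kilogram, so the duplicate does little against this error. The trial is meant to estimate GWG for a future trial (sections 8.1 and 8.2) and to model its course over pregnancy (section 6.1), so error that can be removed at no cost should be removed.

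The larger stake lies in short intervals. The recommended four-week gain is a band narrower than the recording unit. The Appendix A item that sets whole-kilogram recording also defines the adaptation criterion as gain below, exactly at, or above goal, and it does not name the scale that supplies it. If whole-kilogram weights were used there, or for the zero-gain indicator, rounding alone could change how a woman is classified.

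**Working it through.** The plan gives no figure for measurement error, so there is none to reproduce.

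**Inputs from the documents**
- Recording unit for pre and post clinic weight: 1 kg (Appendix A) = 2.2046 lb.
- Recommended weekly gain (table in section 10.2): overweight 0.5–0.7 lb, obese 0.4–0.6 lb.
- Recommended total gain (Appendix A): overweight 15–25 lb, obese 11–20 lb, so bands 10 and 9 lb wide.
- Assessment interval: 4 weeks (section 6.2).

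**Assumption:** an SD of GWG between 8 and 18 lb. The documents give none.

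**Step 1: rounding error of a pre–post change (certain).** The error of one rounded reading is uniform on ±0.5 kg, with SD 1/√12 = 0.289 kg. The difference of two independent readings has SD √(2/12) = 0.408 kg = 0.90 lb. The worst case is 1 kg, or 2.2 lb.

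Added variance as a share of the GWG variance:
- SD 8 lb: 0.90²/8² = 0.81/64 = 1.3%
- SD 12 lb: 0.81/144 = 0.56%
- SD 18 lb: 0.81/324 = 0.25%

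At 0.1-kg recording the SD of a change falls tenfold, to 0.04 kg (0.09 lb), and the added variance to about 0.01% or less.

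**Step 2: four-week change, if session weights are also whole kilograms (conditional).**
- Overweight band: 4 × 0.5 to 4 × 0.7 = 2.0–2.8 lb. Obese band: 4 × 0.4 to 4 × 0.6 = 1.6–2.4 lb. Each is 0.8 lb wide, against a unit of 2.2 lb.
- For a true gain g below 1 kg and a starting weight uniform within the kilogram, P(recorded as zero) = 1 − g/2.2046, with g in lb.
  - g = 1.6 lb (obese lower limit): 1 − 0.726 = 27%.
  - g = 2.0 lb (obese midpoint, overweight lower limit): 1 − 0.907 = 9%.
  - g of 2.2046 lb (1 kg) or more: 0%.
- For a true gain between 1 and 2 kg, P(recorded as 2 kg, or 4.4 lb) = g/2.2046 − 1. At g = 2.8 lb (overweight upper limit) this is 1.270 − 1 = 27%, so a woman at the limit would be recorded above it.

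A simulation of 2,000,000 starting weights gave the same values: 27%, 9% and 27%.

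**Step 3: which weights the conditional part needs.** Whole-kilogram recording is stated only for the pre and post clinic weights, which Appendix C places at gestational weeks 8 and 35. Step 2 needs two further things: that session weights on the standardized scale are rounded the same way, and that they feed the visit-level change or the flags. The documents state neither and exclude neither.

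**The case against.** The strongest reply is about scope. Whole-kilogram recording is attached to two weights 27 weeks apart, and over that span it barely matters. Monitoring is described in terms of daily weights in sections 10.1 and 10.2. Section 10.4 has daily weights reviewed at the weekly sessions and then sets out the weight-loss flag. Section 16.1 requests a laptop so that the instructor can upload home-scale data at those same sessions. The section 10.2 sentence on calculating weight change names no scale. The insufficient-gain indicators are given as examples that lead to consultation and review of several factors, so a rounded zero would not act by itself. The 27% figure also belongs to the bottom edge of the obese band; at its midpoint the figure is 9%.

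Most of this stands. A reader might infer that staff compute interval change from whole-kilogram clinic weights, so that recorded four-week change could only be 0, 2.2 or 4.4 lb and women would be misflagged. The documents do not support that as a statement of fact.

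Two things remain. The pre–post rounding is stated outright and is avoidable. The link to sessions is also plausible: Appendix B puts the session weight in the same row as the pre and post weights, and whole kilograms is the only recording precision that the protocol gives for any weight. The unit may be a slip for a finer one, which the documents cannot settle; that too would call for a correction.

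**Conclusion.** The point holds in two parts of different standing.

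- **Certain and small.** Whole-kilogram recording adds an SD of 0.41 kg (0.9 lb) to each woman's pre–post change. That is about 0.25% to 1.3% of the variance of GWG over an assumed SD of 18 down to 8 lb. It does not threaten the pilot's estimates.
- **Conditional and larger.** If session weights are also rounded to the kilogram and used for interval change, the recommended four-week gain cannot be resolved: a true gain of 1.6 lb is recorded as zero 27% of the time and one of 2.0 lb 9%. Because monitoring is tied mainly to daily home weights, this shows what the protocol leaves open and is not an established error in the flags.

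This is a minor improvement, worth making because it is nearly free.

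**What to change.** 1. In Appendix A, have every weight on the standardized scale (pre, session and post) recorded to the nearest 0.1 kg, and say that the mean of the duplicate readings is analysed. If whole kilograms was a slip, correct it.
2. In Appendix B, state the recording precision of the session weight and of the home scale.
3. In section 6.2 or Appendix A, and in section 10.2, name the weight source that supplies the adaptation assessment, the visit-level weight change and the insufficient-gain indicators.

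The scale and the readings stay the same, so the cost is a few lines of text and one more digit on the form. The rounding SD of a change falls from 0.90 to about 0.09 lb.

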2.3 Study Rationale

The research proposed here will establish the dosage of components needed to impact GWG and develop an efficient (optimized) intervention to effectively manage GWG in OW/OPBW before a randomized controlled trial (RCT) can be implemented.

Rationale for expanding recruitment to normal weight (body mass index 18.0 to 23.9) women: this control-only alternative will be offered to women who are not eligible for the intervention study because their body mass index is below the current cut-off of 24.0. The purpose of extending the control group is to fulfill the target enrollment for the ancillary grant (1R56HL126799-01).

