3.0 Inclusion and Exclusion Criteria

3.1 Inclusion Criteria

- Pregnant women
- Overweight or obese [body mass index range 24- >40 (if BMI is > 40, consultation with woman's health care provider (PCP/OBGYN) will be made to determine eligibility and ensure she does not have any contraindications to exercise) PI [name] will have

communication with [name] from MNPG to give information on the woman. We also have a physician consent form (see Physician Patient Consent to Participate in documents) that the physician will complete as to whether the woman is eligible or not eligible to participate.

- Normal weight women with a body mass index range of 18.0 to 23.9 can be enrolled in to the study as control participants (same measures of data collection, no opportunity for intervention).
- Ages 18-40 years [based on our pilot data this group comprises >85% of the live births in Central Pennsylvania]
- 1st, 2nd or 3rd pregnancy 6-16 weeks gestation
- Able to read, understand, and speak English
- Residing in and around State College, PA
- 1st and 2nd time pregnant mothers [none or one other live or still born, biological children > 25 weeks gestation prior to this pregnancy; it may be conceivable that a woman has a blended family due to a mixed marriage and she will not be excluded if she is a parent to a guardian, foster child, or step child]
- Access to a computer or willingness to come onsite to complete study materials
- Infants born to participants who are 6-10 weeks old

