Accessing Prenatal and Labor/Delivery Data. After study completion, with subject's HIPAA authorization, we will access their medical record data for prenatal (e.g., gestational weight gain, diagnosis of gestational diabetes, complications, etc.) and labor/delivery data. A subject can choose to not allow us to have access – and she can decide to provide the health information she wants to share. A study staff member will work with the subject's OBGYN provider to coordinate access to this data (e.g., electronic medical record access or hard copy of the prenatal and labor/delivery data).

Visit D Postpartum Assessment and Weekly Measurements At 6-8 weeks postpartum, women will return to Noll Lab to complete maternal and infant measurements; they will be expected to bring their infant with them to this session but if they do not want their infant involved, they will still be asked to complete the measurements asked of them. Women will be asked to (1) weigh themselves using the Aria Wi-Fi scale for a 7-day period, (2) wear the Jawbone wrist-worn activity monitor for a 7-day period, (3) complete one Breezing device measurement, (4) provide one urine sample, (5) one BodPod assessment, and (6) take photographs of their food for 2 weekdays and 1 weekend day. While on site, the women's babies will (1) complete a PeaPod measurement. The baby's test takes place in a similar small space with a window where the baby can be seen the entire time. The baby's test is two minutes long, and typically only one test is needed. We can stop the test at any point. The baby will be placed in the warm measurement space free of any clothing or blankets. The PeaPod measurement is similar to the BodPod measurement.

Postpartum Survey Women will be emailed a link to a postpartum survey 2-6 weeks after delivery. Women will complete this survey on REDCap. Women without access to the Internet will be sent the survey via the mail. The survey has been uploaded as study materials.

- R56: The additional normal weight (body mass index 18.0-23.9) subjects will be assigned to the control group (i.e. will not be randomized); these subjects will complete all measures to expand data collection of indicators of fetal growth as well as self-report data.

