10.2 Data that are reviewed

Definition of adverse event. An adverse event shall be defined as any detrimental change in the participant's condition, whether it is related to study interventions, study outcomes, or to another unrelated illness.

Adverse events unrelated to the study interventions. Adverse events due to illnesses unrelated to study interventions may be grounds for withdrawal if the illness is considered significant by the study investigators or if the participant is no longer able to effectively participate in the study. A significant illness would be one that would compromise the women's ability to function normally and thrive such as the diagnosis of a disease requiring ongoing and intensive treatment and/or one requiring repeated hospitalizations or physician visits. Subjects experiencing routine, minor, self-limited acute illnesses that typically occur during pregnancy and do not affect long-term growth will not be recorded, and the women will continue to participate in the study. Examples of minor illnesses include bronchiolitis, upper respiratory infections, and urinary tract infections. Examples of minor unanticipated events from the PA session may be minor aches, a cold, feeling uncomfortable, mild nausea. Medications for acute, self-limited illnesses such as those stated above will not be recorded, but chronic medication use (≥ 1 month) will be recorded. Further surgical conditions that could impact HE, PA and GWG will be recorded and if the participant's physician determines that these conditions can affect prenatal weight gain, the participant will be withdrawn from the study.

Documentation of an AE unrelated to the study interventions that are not considered minor illnesses and those that can significantly affect the baby will be recorded on the AE form and reported to the IRB. See the protocol for unexpected or adverse events for actions and reporting of the unexpected events and AEs.

Adverse events potentially related to the study interventions. While the majority of OW/OBPW have excessive GWG (over the threshold ranges for prepregnancy weight category as illustrated in the table below:

Institute of Medicine Weight Gain Recommendations for Pregnancy

Prepregnancy Weight Category	Body Mass Index*	Recommended Range of Total Weight (lb)	Recommended Rates of Weight Gain† in the
			Second and Third Trimesters (lb)
Underweight	Less than 18.5	28–40	1 (1–1.3)
Normal Weight	18.5–24.9	25–35	1 (0.8–1)

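### Randomised women with BMI 24.0-24.9 are labelled overweight, but the protocol's own table classes them as normal weight, and Appendix A gives them no matching weight-gain target

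*Combined protocol and SAP*

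**What the plan says.** **Eligibility.** Section 3.1 admits women under the heading "Overweight or obese [body mass index range 24- >40". Section 2.3 confirms the boundary: the control-only option is for women who cannot enter the intervention study "because their body mass index is below the current cut-off of 24.0". Section 6.2 keeps only the band below that out of randomisation: "The additional normal weight (body mass index 18.0-23.9) subjects will be assigned to the control group (i.e. will not be randomized").

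**Guideline.** Section 10.2 prints a table titled "Institute of Medicine Weight Gain Recommendations for Pregnancy". Its normal-weight row covers BMI 18.5-24.9 (25-35 lb in total, 0.8-1 lb per week in the second and third trimesters). Its overweight row starts at BMI 25 (15-25 lb, 0.5-0.7 lb per week). Its categories are by prepregnancy weight.

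**Goal and its use.** Appendix A states that "target weight gain will be determined for each woman based on BMI status (OW = 15-25 lb, OB = 11-20 lb"). It gives that goal a function: "For the criterion measure to determine when to adapt the intervention, weight gain will be calculated" to see whether a woman is below, at or above it. Section 6.2 supplies the action: "If weight gain has succeeded the recommended amount, participants will be adapted up to a new level of intervention" (evidently meaning exceeded), and then "After every 4 weeks, an assessment will be performed and adaptations up will be made if necessary". Appendix C places the decision points after gestational weeks 12, 16, 20, 24 and 28.

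**The concern.** The eligibility boundary and the guideline boundary differ by one BMI unit, and the goal that drives the adaptive rule falls into the gap. A woman of BMI 24.0-24.9 is randomised as overweight or obese, yet the protocol's table gives her a normal-weight recommendation. Appendix A lists no goal for that row. Staff must choose, and the label in section 3.1 points to the overweight goal.

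That choice matters in the intervention arm. Step-ups add exercise sessions, portion control and, at the higher levels, meal replacement. With the overweight goal, a woman who gains what the table recommends may be recorded as exceeding her goal and moved to a higher weight-limiting dose. Section 12.1 names better adherence to this same guideline as an expected benefit, so for her the rule would pull the other way. The dosing data are also meant to inform the later trial.

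Section 10.2 has a related, smaller mismatch. It uses 0.5 lb per week as the contextual reference for all overweight and obese participants. That suits the overweight and obese rows, but it is below the 0.8 lb lower limit in the normal-weight row.

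**Working it through.** **1. Classification.** BMI 24.0-24.9 lies wholly inside the randomised range (24 and above) and wholly outside the control-only range (18.0-23.9). It lies wholly inside the table's normal-weight band (18.5-24.9) and wholly outside its overweight band (25-29.9).

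**2. Total goal.** The two goals in Appendix A reproduce the table's overweight and obese rows exactly (15-25 and 11-20 lb), so both come from the same guideline. For BMI 24.0-24.9 the table gives 25-35 lb. Against the overweight goal:
- lower ends: 25 - 15 = 10 lb
- upper ends: 35 - 25 = 10 lb
- the ranges meet only at 25 lb, so any total that the table recommends is 0-10 lb above the overweight ceiling.

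This step needs no assumption beyond use of the overweight goal.

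**3. Goal at a decision point.** Appendix A gives totals only and no conversion to a 4-week cycle. At the table's 0.8-1 lb per week she gains 4 × 0.8 = 3.2 to 4 × 1.0 = 4.0 lb per cycle. Four possible readings of the overweight maximum are set out below. They take the second and third trimesters as the 27 weeks from the end of week 13 to week 40, and the first-trimester gain as 1.1-4.4 lb from the table's footnote.

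| Reading | Overweight maximum (lb) | Her gain (lb) | Difference (lb) |
|---|---|---|---|
| Overweight weekly rate, per cycle | 4 × 0.7 = 2.8 | 3.2-4.0 | +0.4 to +1.2 |
| 25 lb spread evenly over 40 weeks, per cycle | 25/40 × 4 = 2.5 | 3.2-4.0 | +0.7 to +1.5 |
| 25 lb less first-trimester gain, over 27 weeks, per cycle | (25 - 4.4)/27 × 4 = 3.05 to (25 - 1.1)/27 × 4 = 3.54 | 3.2-4.0 | -0.34 to +0.95 |
| Cumulative at week 28 (15 weeks after week 13) | 4.4 + 0.7 × 15 = 14.9 | 1.1 + 0.8 × 15 = 13.1 to 4.4 + 1.0 × 15 = 19.4 | -1.8 to +4.5 |

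On the first two readings she is always above goal. On the last two she may be above or below it.

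**4. Weekly reference in section 10.2.** 0.5/0.8 = 62.5% of her lower limit. Steady gain at 0.5 lb for 27 weeks is 13.5 lb. Adding 1.1-4.4 lb gives 14.6-17.9 lb, which is 7.1-10.4 lb short of 25 lb.

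**5. Sample size.** Section 8.1 reproduces: 12/(1 - 0.20) = 15 per group, 30 in total. Nothing above changes it.

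**The case against.** The best defence is that the gap is an omitted line and not a conflict. Appendix A bases the goal on each woman's BMI status and cites the same guideline, so staff could take the table's row for her own BMI and read the parenthesis as listing only the two named groups. The opposite defence is also coherent: 24.0 and 23.9 are used consistently, so the study may mean to treat everyone from 24 as overweight. Neither defence settles the matter. The text states neither intention, the two lead to goals 10 lb apart, and the second contradicts the table in section 10.2.

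Other objections succeed against stronger readings:
- A reader might infer that such a woman would be stepped up at every decision point after the first trimester. The documents do not support that, because the conversion to a cycle goal is not given and two of the four readings above allow her to be at or below goal. At 0.8 lb per week her total is 0.8 × 27 + 1.1 = 22.7 to 0.8 × 27 + 4.4 = 26.0 lb, largely within the overweight ceiling.
- A reader might infer that the 0.5 lb reference would hide insufficient gain. Section 10.2 uses it for context beside clinical judgement. Its example indicators are loss above 3% in a week or no gain over a 4-week cycle. Obstetric consultation, provider alerts and weight review at least twice monthly do not rest on 0.5 lb.
- A reader might want a count of affected women. The documents give no BMI distribution, and the number could be zero.

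The consequence is also bounded. The activity follows obstetric guidance, the meals meet dietary guidelines for pregnancy, and section 8.2 presents a feasibility pilot that is not powered for definitive claims.

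**Conclusion.** The point holds as an internal inconsistency in a decision rule. Women of BMI 24.0-24.9 can be randomised under an overweight label, the protocol's guideline table recommends 25-35 lb for them, and the appendix that sets the step-up goal offers only 15-25 or 11-20 lb. If the label decides, the goal is 10 lb too low at both ends and its ceiling is the guideline's floor. A recommended gain can therefore trigger a step-up in the intervention arm.

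The 10 lb figure rests only on the assumption that the overweight goal is applied. The frequency of unwarranted step-ups and the number of women affected cannot be derived from the documents. The weekly reference is a secondary point, since it is contextual. The inconsistency does not undermine the randomised comparison, the measurement of raw weight gain or the sample size. It does affect the dose that some women may receive and any gain standardised to target.

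Section 3.1 does not say whether eligibility BMI is prepregnancy or measured at entry (6-16 weeks). If it is measured at entry, women with a prepregnancy BMI below 24 could also be randomised, so a remedy limited to 24.0-24.9 would miss some of them.

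**What to change.** - **Appendix A:** state that the goal follows the section 10.2 table by prepregnancy BMI. Beside the two existing goals add: *prepregnancy BMI below 25 (randomised women) = 25-35 lb*, and use this as the goal for step-up decisions.
- **Section 10.2:** for these women, read second- and third-trimester weekly gain against 0.8-1 lb instead of 0.5 lb, as a prompt for clinical review and not as a removal rule.
- **Reporting:** give, by arm, the number of randomised women with BMI below 25.

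**Alternative,** if these women are not meant to receive the intervention: move the cut-off in sections 2.3 and 3.1 to 25.0, extend the non-randomised control range to 24.9, and say that the cut-off refers to prepregnancy BMI.

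**Cost.** The first option adds a third goal to the adaptation rule and one monitoring reference. Both use values already printed in the protocol, and weights are already collected daily. Prepregnancy weight must be known when the goal is set. Appendix A takes it from clinical records, while section 6.2 describes record access after study completion, so it should be recorded at the baseline visit. The alternative slightly narrows the pool for randomisation. Neither option changes the target of 30.
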